Research Proposal

Use of a “flash-free” adhesive resin for orthodontic bracket bonding: a clinical study of bonding time, bond survival, and adhesive remnant cleanup

[name], Dr med dent, PhD, [name], MS

Division of Orthodontics, Department of Developmental and Surgical Sciences, University of Minnesota

Background:

The time required for bracket bonding and cleanup of remnant adhesive from the enamel surface after bracket debonding are important determinants of the duration of the two longest appointments during orthodontic treatment. The development of “flash-free” adhesives resin for orthodontic bracket bonding, which is due on the market in the near future, now promises a decrease in chair time for both patient and orthodontist. However, questions remain regarding the bonding time and bond survival of orthodontic brackets bonded using these adhesives, and the time required for adhesive remnant cleanup. These factors will be critical in determining the acceptance of these new “flash-free” adhesive resins in the orthodontic community.

Purpose:

The purpose of this study is to compare (1) bonding time, (2) bond survival, (3) amount of adhesive remaining on the tooth surface after bracket debonding, and (4) time required for adhesive remnant cleanup between a new “flash-free” and a conventional adhesive resin for orthodontic bracket bonding.

Methods:

Thirty consecutive patients presenting for comprehensive orthodontic treatment with fixed appliances at the University of Minnesota, who are willing to participate, will be included in the initial study. Selection criteria will include full permanent dentition through the first molars, teeth with sound, non-carious buccal enamel and no pretreatment with chemical agents such as hydrogen peroxide, and no previous orthodontic treatment with fixed appliances. The patients will have their maxillary incisors, canines, and premolars bonded with ceramic orthodontic brackets pre-coated with a “flash-free” adhesive resin (Clarity Advanced Brackets “flash-free”, 3M Unitek Monrovia, CA, USA) on one side and a conventional adhesive resin (Clarity Advanced Brackets APC II, 3M Unitek) on the other side. The side allocation and order of bonding will be randomized for each patient.

A total of ten calibrated clinicians will perform the clinical procedures together with their dental assistants.

Bonding time

The patient's teeth will be polished using a fluoride-free prophylaxis paste (Topex Prep&Polish, Sultan Healthcare, Hackensack, NJ, USA) on a rubber cup attached to a low speed handpiece, etched with 35% phosphoric acid (Temrex, Freeport, NY, USA) for 30 seconds, rinsed with water, air-dried, and primed using a conventional primer (Transbond Light Cure Adhesive Primer, 3M Unitek) following the manufacturer's instructions. The teeth will then be bonded according to the predetermined protocol with the "flash-free" product on one side (group 1) and the conventional (APC II) product on the other side (group 2) using a direct bonding technique. Excessive adhesive in group 2 will be removed with a sharp scaler. The adhesive will be light cured for 20 seconds (5 seconds on each side of the bracket) with a light-emitting diode polymerization device (Ortholux LED, 3M Unitek). The distance between the exit window and the adhesive surface will be maintained at less than 5 mm in order to obtain adequate polymerization. The time taken to bond each side will be timed to the nearest second using a digital stopwatch.

Bond survival

Possible bond failure will be recorded at standardized intervals of four weeks. In case of a bond failure, the patients will be asked about a possible explanation for the bond failure. Bond failure as a consequence of habits and trauma will be excluded from the evaluation.

Adhesive remnant cleanup

After completion of orthodontic treatment, the brackets will be debonded following the manufacturer's instructions. The order of debonding will be randomized for each patient. Once the brackets are debonded, the adhesive remnant index (ARI; Årtun and Bergland, 1984) will be scored under $\times 10$ magnification using an optical microscope (MVX10, Olympus, Tokyo, Japan).

Remaining adhesive will be removed from the tooth surfaces using a tungsten carbide finishing bur (H 283-21-012, Brasseler, Savannah, GA, USA) in a low speed handpiece until the enamel has regained its natural gloss (David *et al.*, 2002). Satisfactory removal of the remnant adhesive will be verified by visual inspection under a dental operating light. The time taken to clean up the residual adhesive in each quadrant will be timed to the nearest second using a digital stopwatch.

Statistical analysis

Descriptive statistics will be applied to the data to obtain mean values and standard deviations, and the data will be tested for normality (Kolmogorov-Smirnov test). Differences between the groups will be tested for statistical significance using a Student's *t*-test if the data are normally distributed and a Mann-Whitney U test if the data are non-normally distributed. Bracket survival times will be compared using a Cox's *F* test. A Cochran-Armitage test will be used to determine if there is an association between group membership and ARI. For all tests, *P*-values of less than 0.05 will be considered statistically significant.

Approval:

Approval to conduct this study will be obtained from the Institutional Review Board at the University of Minnesota. Informed consent will be obtained from all participating patients. In case of minors, consent will be obtained from a parent or guardian; assent will be obtained from the minor.

Anticipated outcomes:

Following completion of this study it is expected that significant information will be gained regarding the following:

1. The time required for direct bracket bonding with a “flash-free” orthodontic adhesive resin compared to a conventional adhesive resin together with a possible decrease in chair time when using a “flash-free” product.
2. Bond survival of brackets bonded with a “flash-free” orthodontic adhesive resin compared to a conventional adhesive resin.
3. The amount of adhesive remaining on the tooth surface after bracket debonding using the above products.
4. The time required for adhesive remnant cleanup using the above products and possible decrease in chair time when using a “flash-free” product.
5. An independent assessment of the clinical performance, suitable for peer-reviewed publication, of a new “flash-free” orthodontic adhesive resin.

References:

Årtun J, Bergland S (1984). Clinical trials with crystal growth conditioning as an alternative to acid-etch enamel pretreatment. *Am J Orthod* 85:333–340.

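### Side and bonding order are randomised patient by patient with no balancing described and no side or order term in the analysis, which leaves avoidable chance variation in a 30-patient timing comparison

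*Combined protocol and SAP*

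**What the plan says.** The study is split-mouth: each patient receives the flash-free adhesive on one side of the upper arch and the conventional adhesive on the other. Methods sets the size as "Thirty consecutive patients presenting for comprehensive orthodontic treatment with fixed appliances at the University of Minnesota, who are willing to participate". Allocation is covered by one sentence: "The side allocation and order of bonding will be randomized for each patient". The same section says "A total of ten calibrated clinicians will perform the clinical procedures together with their dental assistants", without giving the number of patients per clinician or saying that one clinician bonds both sides of a patient.

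Under Bonding time, "The teeth will then be bonded according to the predetermined protocol", but the content of that protocol is not given. The outcome is a stopwatch time per side: "The time taken to bond each side will be timed to the nearest second using a digital stopwatch". Under Adhesive remnant cleanup, "The order of debonding will be randomized for each patient", again with no balancing described.

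Under Statistical analysis, group differences are to be "tested for statistical significance using a Student's *t*-test if the data are normally distributed and a Mann-Whitney U test" otherwise. No paired form is specified, and there is no term for side, order or operator. The plan does not describe sequence generation, blocking, stratification or concealment.

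**The concern.** Bonding time is the first comparison listed under Purpose and supports a chair-time claim under Anticipated outcomes. The time for one side may depend on the operator's access to that quadrant and on whether that side was done first or second. Comparing the two sides of one mouth removes the patient's level and, if one clinician does both sides, that clinician's general speed. It does not remove a right-left or first-second difference. In the realised data, those cancel only as far as side and order are balanced against adhesive.

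The plan randomises both factors, so it already treats them as needing control. With only 30 patients, simple randomisation can leave a noticeable imbalance, and nothing in the analysis would take it out. The stake is a noisier adhesive difference than the same 30 patients could give, and a result open to the criticism that side or order contributed to it.

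**Working it through.** The plan gives no sample-size calculation, SD or balance figure, so there is nothing of its own to reproduce.

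**Inputs.** 30 patients and ten clinicians (Methods). Assumptions: simple 1:1 randomisation, with side and order independent; three patients per clinician (30/10), since the actual split is not stated.

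**1. How imbalance enters.** Let d be a patient's flash-free minus conventional time: d = A + D_s·x + D_o·z + e. Here A is the adhesive effect. D_s is the right-minus-left difference, and x = +1 if flash-free is on the right, −1 if on the left. D_o is the first-minus-second difference, and z = +1 if flash-free is bonded first, −1 if second. If k of 30 patients have x = +1, the mean of d contains D_s × (2k − 30)/30. The same form holds for order.

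**2. Chance of imbalance, per factor,** as 2 × P(X ≥ k) with X ~ Binomial(30, 0.5):

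| Split | Probability of this or worse | Share carried over |
|---|---|---|
| 19:11 | 0.200 | 8/30 = 0.27 |
| 20:10 | 0.099 | 10/30 = 0.33 |
| 21:9 | 0.043 | 12/30 = 0.40 |

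An exact 15:15 split has probability 0.144. The root-mean-square share is 1/√30 = 0.18. For side or order or both: 19:11 or worse, 1 − (1 − 0.200)² = 0.36; 20:10 or worse, 1 − (1 − 0.099)² = 0.19.

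**3. Illustration only.** If D_s were 10–20% of bonding time (an assumption), a 20:10 split would shift the adhesive difference by 3.3–6.7% of bonding time. The typical shift would be 0.18 × 10–20%, or about 2–4%.

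**4. Bias or noise?** Under randomisation x and z average zero, so the expected value of mean d is A. Simulated type I error of an unadjusted paired t-test was 5.0%, 4.9% and 5.2% with side and order effects of 0, 0.5 and 1 residual SD. The cost is variance. With both effects at 0.5 SD, the variance of d rises by 1 + 0.25 + 0.25 = 1.5 and the standard error by √1.5 = 1.22. At 1 SD the factors are 3 and √3 = 1.73.

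**5. What each remedy achieves** (SD of the carried share; simple randomisation gives 0.183):
- Separate blocks of four per clinician. At three patients the block is never completed and each clinician ends 2:1 on side. SD = √10/30 = 0.105. A 20:10 split needs all ten to lean the same way: 2 × 0.5¹⁰ = 0.2%.
- One trial-wide list in blocks of four. Seven blocks (28 patients) balance exactly. The last two patients fall on the same side with probability 1/3, giving an imbalance of 2. SD = √(4/3)/30 = 0.038. The worst split is 16:14, a share of 2/30 = 0.07.
- A side term in a within-patient model. This removes the carried share. Relative to exact balance on that factor, the standard error grows by 1/√(1 − c²), where c is the share: 6% at 20:10 (c = 1/3) and 1.7% at the typical split (c² = 1/30).

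**6. Single clinicians.** With three patients, the chance that flash-free is always on the same side is 2 × 0.5³ = 0.25. That gives 2.5 of ten clinicians expected, and a chance of at least one of 1 − 0.75¹⁰ = 0.94. Simulations with 0, 1, 2 or 5 left-handed clinicians left the trial-level risk of a 20:10 or worse imbalance at 9.7–10.0%.

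**The case against.** The plan already randomises side, bonding order and debonding order, and each patient receives both adhesives. The adhesive contrast is therefore unbiased in expectation, and side and order effects enter as random variation that a paired standard error reflects. This stands, and it limits the point to precision.

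The plan is also silent on balancing rather than ruling it out. A predetermined balanced list would fit its wording. This stands too: every probability above is conditional on simple randomisation.

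A reader might infer that side, order and operator handedness could easily line up with adhesive. The documents do not support that for the trial as a whole. Complete alignment on side has probability 2 × 0.5³⁰, about 2 in a billion, and even the 1-in-10 split passes on only a third of the effect. Alignment within single clinicians is likely, but no clinician-specific estimate is planned, handedness is not mentioned, and mixed handedness does not change the overall risk.

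Finally, side and order terms alone would recover most of the loss without a new list. That is correct where those terms are used. Blocking then adds little (about 1.7% in standard error per factor at a typical split). It still protects the plain comparison the plan names, and it cannot be added after enrolment.

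**Conclusion.** The point holds as a modest, avoidable loss of precision. No balancing is described, and the named tests have no side or order term. Under simple randomisation in 30 patients, each factor has about a 10% chance of a 20:10 or worse split, which carries one third of any right-left or first-second difference into the adhesive difference. The typical share is 0.18. The size in seconds is unknown, because the documents give no figure for those differences.

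It would go too far to call this confounding or bias, or to say that the plan excludes balancing. The conclusion assumes simple randomisation with side and order independent. The clinician-level figures also assume three patients each. The change is worth making before enrolment because it is nearly free.

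**What to change.** Replace the allocation sentence in Methods with text to this effect:

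> The four combinations (flash-free on the right or left; flash-free bonded first or second) are allocated from one concealed, computer-generated, trial-wide list in permuted blocks of four, spread across clinicians as far as their patient numbers allow. The same clinician bonds both sides of a patient.

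Under Statistical analysis, specify that bonding time is analysed as the within-patient difference, with terms for side and order. Both changes are needed: the list limits the actual imbalance, while the terms keep side and order effects out of the residual variance, where an unadjusted paired test would leave them even with a balanced list. Report the number of patients per clinician and the final side-by-order table. State likewise how debonding order is generated.

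The cost is a few sentences, a different list and a little more analysis work, with no extra patients or visits. Blocks make allocation slightly more predictable, which concealment of the list limits. Exact balance within a clinician is not achievable at about three patients each, and 30 is not a multiple of four, so a 16:14 split on a factor can remain.

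### Bond failures attributed to habits or trauma are excluded after the patient is asked for an explanation, but masking is not addressed and no analysis of all failures is planned

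*Combined protocol and SAP*

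**What the plan says.** Bond survival is item (2) under Purpose. Methods assigns the two adhesives to opposite sides of the upper arch in the same patient: "The side allocation and order of bonding will be randomized for each patient".

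Methods, Bond survival, sets out how failures are handled:

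- Timing: "Possible bond failure will be recorded at standardized intervals of four weeks". The person who records is not named.
- Cause: "In case of a bond failure, the patients will be asked about a possible explanation for the bond failure".
- Exclusion: "Bond failure as a consequence of habits and trauma will be excluded from the evaluation". No criteria are given for a habit or trauma failure, and nobody is named to decide.

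Statistical analysis names one test for bracket survival times, Cox's F test, and mentions no second analysis that keeps the excluded failures. Neither section says whether patient, parent, clinician or recorder is unaware of the side. Methods, Bonding time, describes one procedural difference between the sides: "Excessive adhesive in group 2 will be removed with a sharp scaler".

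**The concern.** Bracket detachment is close to an objective event, so masking may seem unimportant for this outcome. The exclusion rule changes that. Whether a detached bracket enters the analysis depends on a judgement of cause. That judgement draws on an explanation given after the event, with no written criteria. Anyone who knows the side can be influenced by it, knowingly or not. A patient may explain a failure on the new product's side differently, and a clinician who bonded the teeth may probe or interpret the answer differently.

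Randomising the side makes the two sides alike in expectation at bonding. It does not protect a classification made later by people who may know the allocation. At stake is a difference in bond survival that comes from attribution and not from the adhesive, or a real difference that is hidden. Few failures are likely, so a handful of reclassified brackets could carry weight.

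**Working it through.** The plan states no failure rate, event count or power for bond survival, so there is no figure to reproduce. What follows is an illustration.

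**Inputs from the document (Methods).** There are 30 patients. Each side has 2 incisors, 1 canine and 2 premolars, which is 5 brackets. This gives 30 × 5 = 150 brackets per adhesive, or fewer if teeth are missing.

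**Assumed inputs.** True failure risk *p* is the same on both sides, from 2% to 10%. The share of failures put down to habits or trauma is *a* on one side and *b* on the other.

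**True failures per side** = 150 × *p*: 150 × 0.02 = 3, and 150 × 0.10 = 15.

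**Counted-failure ratio with no true difference** = (1 − *b*)/(1 − *a*). The risk *p* cancels.

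- Equal shares, 30% and 30%: 0.70/0.70 = 1.00
- 20% and 30%: 0.70/0.80 = 0.875, or 1.14 in the other direction
- 20% and 40%: 0.60/0.80 = 0.75, or 1.33
- 10% and 50%: 0.50/0.90 = 0.56, or 1.80

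**In brackets**, the gap between sides is 150 × *p* × (*b* − *a*). For 20% and 40% it is 3 × 0.20 = 0.6 at *p* = 2%, and 15 × 0.20 = 3 at *p* = 10%.

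**Chance of a significant result despite no true difference.** This uses a normal approximation for two proportions, two-sided 0.05, both tails counted and brackets treated as independent. With counted risks π₁ = *p*(1 − *a*) and π₂ = *p*(1 − *b*), d = π₁ − π₂ and π̄ their mean:

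- SE₀ = √(2π̄(1 − π̄)/150)
- SE₁ = √(π₁(1 − π₁)/150 + π₂(1 − π₂)/150)
- chance = Φ((d − 1.96·SE₀)/SE₁) + Φ((−d − 1.96·SE₀)/SE₁)

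Worked case, *p* = 10% with 20% and 40% excluded: π₁ = 0.08, π₂ = 0.06, d = 0.02, SE₀ = 0.02946, SE₁ = 0.02944. The two terms are 0.100 and 0.004, so the chance is 10.4%.

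| Assumed *p* | 20% / 30% | 20% / 40% | 10% / 50% |
|---|---|---|---|
| 2% | 5.2% | 6.0% | 9.1% |
| 3% | 5.4% | 6.5% | 11.2% |
| 5% | 5.6% | 7.6% | 15.6% |
| 10% | 6.2% | 10.4% | 27.3% |

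The approximation is rough with so few events, it ignores clustering of brackets within patients, and it stands in for the planned survival test.

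**Counting all failures.** With equal true risk the expected ratio is 15/15 (or 3/3) = 1.00 whatever *a* and *b* are, because attribution no longer enters.

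**The case against.** Much of the case on the other side stands.

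- **Silence is not unmasking.** A reader might infer that patients know which side has the new product. The document does not say so. It neither masks nor unmasks them, and the consent form, which might settle what families are told, is not in the text reviewed. What can be said is that masking is not addressed.
- **The patient is asked, but does not necessarily decide.** A reader might infer that the patient's word alone settles whether a failure counts. The text gives only a source of information. Who decides, and how, is unstated. A clinician who knows the side is at least as likely a source of bias, so a remedy aimed only at patients would fall short.
- **Chewing is not in the plan.** A reader might go further and suppose that patients spare one side when chewing, which would change the failures themselves. The document mentions neither chewing nor load. The argument needs patients to learn the side, remember it, distrust one product and shift load mostly in the same direction relative to the adhesive. Randomising the side already balances habitual preference on average. This point does not rest on it.
- **The effect is small in brackets.** A 20%/30% split moves 0.3 to 1.5 failures and leaves the error rate at about 5-6%. This is right, and it limits the size of the claim.
- **Masking the patient is not easy.** The scaler is used in group 2 only, so an attentive patient can tell the sides apart at bonding. Noticing a difference is not the same as knowing which product it denotes, but the protection is partial.

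These objections narrow the point. They do not close the gap left by an exclusion without criteria, made by people who may know the side, with no analysis that avoids it.

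**Conclusion.** The concern holds in a limited form. A named outcome depends on a post-event judgement of cause for which the plan gives no criteria, decider, masking or all-failure comparison. Attribution that differs by side could bias bond survival in either direction.

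Under the assumptions above, a 20%/40% split yields a ratio of 0.75 or 1.33 from attribution alone. The false-positive rate rises only modestly, to about 6-10%. It reaches 9-27% at the more extreme 10%/50% split. The failure risks and exclusion shares are assumed, and nothing in the document shows that attribution would in fact differ by side.

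The change is worth making because it costs almost nothing, not because a large bias has been shown.

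**What to change.** 1. In Methods, state that patient and parent are not told which side received which adhesive until debonding is complete, and word the consent form to match.
2. In Methods, Bond survival, add written criteria for a habit or trauma failure. Require that the patient's explanation is recorded and the cause classified before the allocation is consulted, where feasible by existing staff who did not bond that patient.
3. In Statistical analysis, prespecify a comparison counting all bond failures regardless of cause, reported alongside the analysis with exclusions. Because side is randomised, true habit and trauma failures should fall equally on both adhesives on average. Including them may pull a real difference towards no effect, but does not favour either product.

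The cost is a few sentences in the protocol and consent form, a short list of criteria, and one extra analysis of data already collected. No visit or procedure is added. The small downside is that masking stays imperfect because of the scaler step. The all-failure comparison is the safeguard on attribution that does not depend on masking.

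### Bonding and cleanup times are compared with no patient or clinician term, so the error bars on the adhesive difference can be too wide or too narrow; pairing alone cures only the first

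*Combined protocol and SAP*

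**What the plan says.** The Methods section enrols "Thirty consecutive patients presenting for comprehensive orthodontic treatment with fixed appliances at the University of Minnesota". Each has one maxillary side bonded with each adhesive, and "The side allocation and order of bonding will be randomized for each patient". On who does the work it says only: "A total of ten calibrated clinicians will perform the clinical procedures together with their dental assistants". It does not give the number of patients per clinician, say that one clinician does both sides of a patient, or say that the clinician is recorded.

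The two time outcomes are measured by side. Under Bonding time: "The time taken to bond each side will be timed to the nearest second using a digital stopwatch". Under Adhesive remnant cleanup: "The time taken to clean up the residual adhesive in each quadrant will be timed to the nearest second using a digital stopwatch". The same section adds "The order of debonding will be randomized for each patient".

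Under Statistical analysis, "Differences between the groups will be tested for statistical significance" by Student's t or, for non-normal data, Mann-Whitney U. Neither is described as paired. Mann-Whitney U is a test for two independent samples. No test in the section has a patient or clinician term.

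**The concern.** The design has two layers of dependence that the named tests ignore.

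- **Two sides in one patient.** They share the patient and, presumably, the operator. That shared variation cancels from the difference between adhesives but stays in the standard error of an unpaired test.
- **Several patients under one clinician.** If the adhesive effect itself differs between clinicians, the differences from one clinician's patients resemble each other. The protocol supplies a reason to expect this: scaler removal of excess adhesive is done in group 2 only, so a clinician's speed and care at that step change the difference and not just the overall level. Cleanup ends on a visual judgement of the enamel, which could also vary by clinician.

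At stake is the chair-time claim. An interval that is too wide may miss a real saving. One that is too narrow may declare a saving that rests on which ten clinicians took part.

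**Working it through.** **Inputs from the documents:** 30 patients, 10 clinicians, 30/10 = 3 patients each on average, two times per patient per outcome, significance level 0.05. Sidedness is not stated; two-sided is assumed.

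**Not in the documents, so assumed and shown as ranges:** the operator, patient and residual standard deviations, and the clustering of the differences. The plan has no sample-size or power figure to reproduce.

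**Model.** Time = operator + patient + adhesive + operator-by-adhesive + residual. Set the residual SD per side to 1. Let s_o and s_p be the operator and patient SDs, and s_i the SD across clinicians of the adhesive effect. One clinician is taken to do both sides.

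- Intraclass correlation (ICC) of the paired differences: ρ = s_i² / (s_i² + 2).
- True variance of the mean difference: (s_i² + 2)/30 × [1 + (3 − 1)ρ]. Neither s_o nor s_p appears.
- Variance used by the unpaired t-test: about 2(s_o² + s_p² + s_i²/4 + 1)/30. Both appear, and the factor 1 + 2ρ is missing.

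**Step 1: adhesive effect the same for every clinician (s_i = 0).** The true standard error is √(2/30) = 0.258 whatever the operators' speeds. In simulation a paired t-test holds 4.9–5.0%. The unpaired test reports an average standard error of:

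- 0.355 at s_o = 1, s_p = 0 (type I error 0.9%);
- 0.439 at s_o = 1, s_p = 1 (0.2%);
- 0.608 at s_o = 2, s_p = 1 (0.01%).

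Here the planned error bars are too wide.

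**Step 2: adhesive effect differs by clinician, paired t-test ignoring clinician.** Equal loads of three.

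| Assumed ICC | Design effect 1 + 2ρ | Standard error should be multiplied by | Effective patients | True type I error |
|---|---|---|---|---|
| 0 | 1.0 | 1.00 | 30 | 5% |
| 0.1 | 1.2 | 1.10 | 25 | about 7% |
| 0.3 | 1.6 | 1.26 | 18.8 | about 12% |
| 0.5 | 2.0 | 1.41 | 15 | about 17% |

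With an illustrative uneven split of 8, 6, 4, 3, 3, 2, 1, 1, 1, 1 (sum 30), the errors at 0.1 / 0.3 / 0.5 are about 9% / 18% / 26%.

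**Step 3: the same clustering, unpaired t-test as named.** Simulated type I error, equal loads:

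| s_o, s_p | ICC 0.1 | ICC 0.3 | ICC 0.5 |
|---|---|---|---|
| 0, 0 | 8% | 15% | 23% |
| 1, 0 | 2.3% | 6.1% | 13.3% |
| 1, 1 | 0.5% | 2.5% | 7.2% |
| 2, 1 | 0.04% | 0.4% | 2.2% |

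These spread the clinician variation over both sides. Confining it to group 2, at ICC 0.3, gives about 12%, 5.4% and 2.2% in the first three rows.

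**Break-even.** The two variances are equal when 2(V + s_i²/4 + 1) = (s_i² + 2)(1 + 2ρ), with V = s_o² + s_p². At ρ = 0.3, s_i² = 0.6/0.7 = 0.857. The right side is 2.857 × 1.6 = 4.571, so V = 4.571/2 − 1.214 = 1.07. Above about 1.07 times the residual variance, the planned standard error is too wide; below it, too narrow.

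**Step 4: price of a simple remedy.** A one-sample t-test on the ten clinician means holds about 5% with equal loads. If there is no clinician variation, and the paired t-test on 30 differences has 80% power, the clinician-means test has about 73% with equal loads but only about 53% with the uneven split above.

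**The case against.** The strongest defence is the split-mouth design. A reader might infer that because some clinicians are faster than others, the 30 patients are not independent and the error bars must be too small. The documents do not support that step. If one clinician does both sides, which is the natural reading though not stated, a fast or slow operator shifts both times equally and cancels (Step 1). Only variation in the adhesive effect itself matters.

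Nor can one say that the plan as written understates uncertainty. The 7% / 12% / 17% figures belong to a paired test, which the plan does not name. The unpaired test is mostly conservative when operators or patients vary strongly (Step 3).

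Three further objections have weight.

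- The clinicians are described as calibrated, which may make the ICC small. No ICC, operator variance or patient split is given.
- The inflation presumes a target wider than these ten clinicians. The plan does not state this in so many words. However, the Background ties the results to acceptance in the orthodontic community, and the fifth anticipated outcome is a publishable independent assessment.
- If the adhesive makes no difference in any clinician's hands, the paired test keeps its level.

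These limit the size and direction of the claim. They do not supply the missing terms, and the group 2 scaler step keeps variation between clinicians plausible.

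**Conclusion.** The point holds as a two-sided defect. The named tests for bonding and cleanup times can misstate the uncertainty of the adhesive difference in either direction. Too wide is the likelier error where times vary strongly between operators or patients. Too narrow is possible where they do not and the adhesive effect varies by clinician: at an assumed ICC of 0.3, type I error runs from 12–15% with no operator or patient variance down to 0.4% with s_o = 2 and s_p = 1.

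The missing pairing is the clearer fault, but repairing it alone takes away the variance that masked the clustering, leaving about 7% / 12% / 17% at ICC 0.1 / 0.3 / 0.5. These figures rest on assumed ICCs, three patients per clinician, one clinician for both sides, and inference beyond the ten. If two clinicians share a patient, the operator's own speed no longer cancels. The calculations cover the two time outcomes only, not bond survival or the adhesive remnant index.

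**What to change.** 1. Record the clinician's identifier at bonding and again at cleanup.
2. State that one clinician does both sides of a patient at a given visit.
3. Replace the unpaired tests for times with an analysis of the within-patient difference: a mixed model with a random clinician effect on that difference and small-sample degrees of freedom. An operator main effect alone would not do this. Report the mean difference with its 95% confidence interval.
4. Do not use the t-test on ten clinician means unless loads turn out near equal, given its fall to about 53% power under uneven loads.

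The cost is one field on the form and a few sentences in the plan. There are fewer degrees of freedom, and a variance estimated from ten clinicians, some perhaps with a single patient, will be imprecise. The power of the mixed model was not computed here.
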